To summarize, this proposal has various innovative aspects in the investigation of pain amplification in response to insomnia: (1) Taking a mechanistic approach (inflammatory-induced sensitization, pain-inhibitory induced habituation to pain), rather than continuing to characterize the general association between insomnia (or sleep deficiency in general) and pain. (2) Studying inflammatory and pain-inhibitory systems changes within a real-life model consisting of repeated exposure to experimentally-induced insomnia symptoms, rather than studying changes within short-term models of sleep restriction or deprivation of a few days. (3) Investigating the ability of system changes to recover from repeated exposure to experimentally-induced insomnia symptoms, rather than concentrating only on the effects of deficient sleep.

B3. DESCRIPTION OF RESEARCH PROTOCOL

A. Study Design – Overview, Methods, Procedures

Proposed Research Plan.

The overarching hypothesis of this research is that repeated exposure to experimentally-induced insomnia symptoms increases vulnerability to chronic pain by promoting two processes: (1) sensitization of the nociceptive system via a progressive increase of the inflammatory response and (2) decreased habituation to pain via progressive deterioration of the pain-inhibitory response.

This proposal will implement a research design consisting of 3 repetitions of a 4-day episode with 3 nights of experimentally-induced insomnia symptoms followed by 1 night of recovery sleep, thereby resembling frequently observed sleep patterns in individuals suffering from insomnia. I.e., after an interval of 1 to 3 nights of poor sleep, individuals experience a better night of sleep, likely resulting from a buildup of sleep pressure during the insomnia episode^{31,41}. The protocol will end with 4 nights of recovery sleep, in order to statistically model time to obtain full recovery of the inflammatory and pain-inhibitory system. The study will take place under controlled in-laboratory conditions in the Clinical Research Center, in order to ensure maintenance of sleep-wake schedules and minimize the influence of confounding variables such as food or fluid intake, light exposure, body posture and motor activity. Each protocol includes frequent blood draws, urine collections, and the administration of a complex pain testing battery on 8 out of the 18 in-hospital days.

Study Design.

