The Cold Pressor Test (CPT): This test requires the insertion of the hand into an ice-cold water bath (Techne® water baths, Bibby Scientific US, Burlington, NJ) held at a temperature of 3°C. Participants are instructed to leave their hand in the water bath for at least 1 minute and are told that they may remove their hand earlier if the pain gets unbearable. Maximum immersion time will be 3 minutes. Pain intensity and unpleasantness will be rated every 10 sec during the hand immersion, as well as every 10 sec for 2 minutes and 30 seconds post-testing to capture recovery slopes.

Statistical Considerations

Sample size: 34 subjects (including a 32% discontinuation rate) will run in balanced order through the two protocols, each consisting of a 18-day in-hospital stay (separated by an interval of 1 month or more) in order to complete the study with 26 subjects. **Power calculations** for the inflammatory response (aim 1) were estimated using findings coming from sleep restriction models on IL-6 (plasma levels and expression by monocytes). For the pain-inhibitory response (aim 2), we estimated power using the effects of a single episode of sleep disruption on the pain-inhibitory capacity³⁷. For the recovery response (aim 3), we used data from the effects of recovery sleep on IL-6 positive monocytes, as well as on the habituation to pain in the cold pressor test paradigm (data obtained in currently ongoing protocol). For all 3 aims, optimal power will be reached with a sample size of N=26 (see **Table 1**).

Randomization: Block randomization will be used with block sizes of 10, 8, 8, and 8. Each block will have equal numbers of females and males and equal numbers of sequences (1. insomnia induction – control sleep, 2. control sleep – insomnia induction). Randomization will be prepared by the study statistician and the participant will be informed of the sequence on study day 1.

Statistical Analysis:

Table 2 shows the primary outcome variables for aim 1-3, as well as secondary outcome variables used for explorative analysis (not part of aims).

Some of the variables will be measured at different time scales and reduced to the following summary variables: Subjective estimations of emotional and physical well-being assessed every 4 hours during the waking periods (and after each nighttime awakening during insomnia induction nights) of the protocol will be averaged to nighttime and daytime frequency and intensity measures.

Table 2: Outcome variables			

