Outcome variables will be measured on 8 out of the 18 in-hospital protocols (baseline, 2nd experimental insomnia/control night and 4th recovery night of each episode, and 3rd recovery night at end of protocol). The analysis will focus on episode-wise comparison of outcome variables between experimental insomnia and control sleep conditions. Although several forms of linear mixed model will be used, our main analysis will focus on daily summary measures (mean, max, min, slope, AUC, etc.) The models will be constructed as follows: the study has two within factors (measurements over several days and measurements within the same day). Data will be used as it is or the difference between the two experimental conditions by episode will be used in the analysis. The main method of data analysis will employ linear mixed model (repeated measures analysis).

By defining appropriate contrast we can evaluate (i) the difference between experimental insomnia nights and recovery sleep nights for the entire study period, (ii) the difference between days 3 and 6 (day6 minus day3), 7 and 10, and 11 and 14 separately. We expect that each of the contrasts will yield a significantly positive value. These comparisons will show if IL-6 values drops or increases from experimental insomnia nights to recovery sleep nights. Similarly, from the same model, by defining appropriate contrasts, we will evaluate the difference between days 6 and 7, 10 and 11, and 14. These contrasts are expected to be negative. Time will also be used as a continuous variable to test the trend and quadratic effect, and if the above contrast does not suggest strong episode-wise effect but mild increment (or decrease) from one episode to the next. We may also use piece-wise regression with a knot at each episode (and also with just one knot to capture the effect of prolonged recovery towards the end of the experiment). As mentioned earlier, many of the exploratory analysis will be guided by plots and summary assessment of the data. Other inflammatory marker (PEG2, resolvins) will be analyzed in a similar fashion.

Sensitization variables (HPT, PPT, TS) will be analyzed similarly and are expected to mimic the time course of inflammatory variables. Correlation between inflammatory markers and sensitization variables will be evaluating using the Altman-Bland method². The linear mixed model described above can be used to obtain the necessary estimates to compute this correlation.

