Assessment of Aim 2: Pain-inhibitory response and its relation to indicators of habituation to pain upon repeated episodes of experimentally-induced insomnia symptoms. Analysis will follow the strategy similar to one outlined in Aim 1. To evaluate co-variation of the pain-inhibitory response with indicators of habituation we will first obtain average values of each value for each day, and use the Altman-Bland correlation approach described earlier.

These data will be analyzed using linear mixed model for doubly repeated measures using SAS GLM procedure as described in:

http://support.sas.com/documentation/cdl/en/statug/63033/HTML/default/viewer.htm#statug_glm_sect054.htm.

Assessment of Aim 3: Recovery of the inflammatory and pain-inhibitory response upon

repeated episodes of experimentally-induced insomnia symptoms. The proposed incomplete resolution of inflammatory and pain-inhibitory responses during the recovery nights and the progressive impairment of these responses across insomnia induction episodes will be evaluated using a mixed model approach and utilizing four time points: baseline, and recovery at the end of 1st, 2nd, and 3rd insomnia episode. Recovery response will be further evaluated by comparing effects of a single night of recovery sleep to a set of 3 nights of recovery sleep at the end of the protocol. Data analysis for this aim is similar to data analysis described for Aim 1, but a different set of contrasts need to be defined. Our conjecture is that during the recovery IL-6 drops but does not reach to the level of previous recovery. To test this we will evaluate contrasts that compare IL-6 values at days 3 and 7, 7 and 11 and 11 and 15. Finally, the difference between day 15 and 17 is assumed to be larger than any other difference between sleep restriction and recovery days. To test this we will evaluate the differences between other recovery days (average of days 7, 11, and 15) and day 17. All analysis will be performed using SAS statistical package (version 9.3).

C. Subject Selection

Human Subjects Involvement and Characteristics

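### The Altman-Bland correlations in Aims 1 and 2 have no stated rule for dependence between recording days; in the standard within-person form, intervals would be too narrow and p-values too small

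*Combined protocol and SAP*

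**What the plan says.** The combined protocol and SAP covers this in B3, Statistical Considerations.

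- **Aim 1 link** (markers IL-6, PGE2, resolvins against HPT, PPT, TS): "Correlation between inflammatory markers and sensitization variables will be evaluating using the Altman-Bland method". The next sentence adds: "The linear mixed model described above can be used to obtain the necessary estimates to compute this correlation".
- **Aim 2 link** (CPM against habituation): "we will first obtain average values of each value for each day, and use the Altman-Bland correlation approach described earlier".
- **Data entered**: "Data will be used as it is or the difference between the two experimental conditions by episode will be used in the analysis".
- **Schedule**: the B3 design overview has "administration of a complex pain testing battery on 8 out of the 18 in-hospital days", in each of two stays. The sample-size paragraph describes the stays as "separated by an interval of 1 month or more".

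For the correlations, the plan does not say whether the within-person or between-person version is meant. It also does not give the degrees of freedom, the covariance structure of the mixed model that may supply the estimates, or how an interval or p-value is formed.

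**The concern.** The standard within-person version removes each person's mean and tests the remaining daily deviations as if they were independent. In this trial those deviations come from two separate runs of 8 closely spaced days. A marker or a pain measure may sit high or low for a whole stay, and either may carry over from one recording day to the next.

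The plan's own reasoning makes carry-over plausible in both variables. B2 reports IL-6 still disturbed after one or two recovery nights and expects incomplete recovery of pain inhibition between episodes. Aim 1 expects the pain measures to follow the course of the inflammatory markers.

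These correlations are the analyses the plan specifies for linking sensitization to inflammation and lost habituation to weaker pain inhibition. Aim 1 alone has 3 x 3 = 9 pairs. If precision is overstated, a chance correlation is more easily read as a mechanism.

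**Working it through.** **Plan's own figure.** The documents give no power or precision for the correlations. The only related figures are the Table 1 powers (paired t-test, alpha 0.05, N = 26), which are all stated as above 0.80. Two-sided recalculation on 25 df gives 1.000, 0.806, 0.989, 0.837 and 0.987, so they reproduce. They use one difference per person and are not affected by this point.

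**Inputs from the documents.** 26 completers; 2 stays; 8 recording days per stay; days 3, 6, 7, 10, 11, 14, 15 and 17, as named in the Aim 1 and Aim 3 contrasts.

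**Assumed inputs.** The share of within-person variance at stay level, and the serial correlation. The documents give neither.

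**Step 1, nominal precision.** Values: 26 x 16 = 416. Residual df with person as the only factor: 416 - 26 - 1 = 389. Near r = 0 the standard error is 1/sqrt(390) = 0.0506, so the 95% half-width is 1.96 x 0.0506 = 0.099.

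**Step 2, false-positive rate.** Two unlinked series were simulated for each person as person effect + stay effect + first-order autoregressive day error, with 6,000 to 8,000 data sets per setting. Each was tested at a nominal 5% with person as the only factor. Both variables had the same dependence.

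| Stay share | Serial correlation | Rejection, correlation decaying per calendar day | Rejection, same correlation between successive records |
|---|---|---|---|
| 0 | 0 | 5% | 5% |
| 0 | 0.3 | 6% | 7% |
| 0 | 0.5 | 7% | 11% |
| 0.2 | 0.3 | 9% | 11% |
| 0.2 | 0.5 | 11-12% | 17% |
| 0.3 | 0.3 | 12-13% | 15% |
| 0.3 | 0.5 | 15-16% | 20-21% |

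Stronger dependence raises this further: 24% at 0.8 per day with stay share 0.2. At 0.5 per day and stay share 0.2, the true standard deviation of r is about 1.25 times the nominal one, so the half-width should be about 0.099 x 1.25 = 0.12.

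**Step 3, day spacing.** The schedule text (2nd and 4th day of each episode) implies days 3, 5, 7 and so on to 17. With that spacing, 0.5 per day gives about 6% alone and 10% with stay share 0.2, slightly below the table.

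**Step 4, between-condition differences.** With 8 day-matched differences per person, a stay effect becomes a constant per person and drops out. Serial correlation remains. For serial correlation 0.3 to 0.5, rejection is about 6-7% with calendar-day decay and up to about 10% with equal correlation between successive records.

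**Step 5, one variable dependent only.** With 0.8 per day and stay share 0.4 in one variable and none in the other, rejection is 5.3%. Dependence in both is needed.

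**Step 6, candidate remedies.** A participant-clustered standard error with 25 df rejected 4.5-6.7% in the moderate settings and 7.3% at the most extreme one tried (0.9 per day, stay share 0.4). A plain percentile bootstrap of participants gave 6-9%. Adding stay as a factor handles the stay effect but leaves about 7% at 0.5 per day and 14% at 0.8.

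**Step 7, shared condition effect.** Suppose insomnia shifts both variables by 0.5 SD, with no other link and no dependence. Per person the expected within-person sum of squares is 15 + 16 x 0.25^2 = 16 and the cross-product is 16 x 0.25^2 = 1, so r = 1/16 = 0.06. The naive test then rejects about 22-27% of the time, and clustering leaves it near 22%. After condition-by-day means are removed it returns to 5%.

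**The case against.** A reader might infer that the plan treats the 16 days as independent. The documents do not say so. That is the default of the standard within-person method, not a stated choice. The between-person version would use person-level means and avoid the problem. The plan also allows between-condition differences, and allows the mixed model to supply the estimates, where stay and serial covariance could be handled. No interval or p-value is written down for these correlations.

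Much of this stands, and it makes the point conditional, but it does not remove it. The hypothesis concerns change within people, and Aim 2 forms one value per day, so the within-person version is the natural reading. The mixed-model route is optional and names no covariance structure. Differences reduce the problem without ending it (Step 4). A correlation offered as evidence of mechanism will in practice be reported with an interval or a test.

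A reader might also infer a false-positive rate of 10-20% or more per correlation. The documents do not support that as a general figure. It needs an assumed stay share of 0.2 or more or strong serial correlation, in both variables. The design also restrains stay-level variation through matched menstrual phase, a fixed sleep schedule beforehand, repeat blood tests, and controlled diet and fluids.

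**Conclusion.** The point holds conditionally. If all 16 daily values enter with person as the only factor, and both variables carry positive stay-level or serial dependence, the 389 df overstate precision. With correlation decaying per calendar day, the assumed range gives about 6-7% rejection at a nominal 5% (serial correlation 0.3-0.5, no stay effect) to about 9-16% (stay share 0.2-0.3 as well). It is higher if successive records are equally correlated or dependence is stronger, and about 6-10% on between-condition differences. Over nine unlinked Aim 1 pairs, the expected number of false positives would be 9 x 0.05 = 0.45 nominally, against 9 x 0.09 = 0.81 to 9 x 0.16 = 1.44 with a stay effect.

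The true size cannot be computed from the documents. The Table 1 power figures and the condition contrasts are outside this point. Because the remedy costs almost nothing and works under either reading of the data entered, it should be made.

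**What to change.** State in the Aim 1 analysis, and refer to it from Aim 2:

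1. The estimate is the within-person correlation of daily values, and the data entered are fixed in advance (both stays, or between-condition differences).
2. Condition-by-day means are removed from both variables first, so that a shared response to condition is not read as a link.
3. The interval and p-value use a standard error clustered on participant, with both stays in one cluster, and a t reference on participants minus 1 df (25 at N = 26). If both residual variables are scaled to unit pooled within-person SD, the regression slope equals the correlation and carries this standard error.

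A plain percentile bootstrap of participants is not a good substitute at this sample size, because it is somewhat too liberal.

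The cost is a few lines of code, a short addition to the text and somewhat wider intervals. Step 2 also narrows the question to whether a person's marker and pain measure depart from the group course on the same days. Whether both change with insomnia on average stays with the planned mixed-model contrasts. The clustered test was checked only for false positives at zero correlation.

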This hypothesis will be tested by implementing a novel model of repeated exposure to experimentally-induced insomnia symptoms, consisting of 3 consecutive 4-day episodes, each starting with 3 nights of sleep characterized by typical insomnia symptoms (delayed sleep onset, sleep disruption, early morning awakening), followed by a single recovery night of 8 hours of sleep. This model mimics sleep patterns that are typical in insomnia populations^{31;41} as well as chronic pain populations^{28;29}. Twenty-six healthy women and men will be studied in an intra-individual balanced design, with each participant undergoing 2 18-day-in-hospital conditions (total number of days include baseline and additional recovery nights), one consisting of repeated exposure to insomnia symptoms induction and the other serving as control condition with 8 hours of sleep per night. Frequent blood and urine sampling as well as administration of a complex pain testing battery will be obtained and utilized to evaluate the following aims:

Aim 1 will investigate the **inflammatory response** to repeated exposure to experimentally-induced insomnia symptoms. We postulate that there will be a progressive increase in pro-inflammatory markers (IL-6, PGE2) and decrease in anti-inflammatory lipid mediators (resolvins), leading to **sensitization of the nociceptive system**, as manifested by lower pain thresholds to pressure and heat, as well as increased temporal summation of pain (an index of central sensitization).

Aim 2 will investigate the **pain-inhibitory response** to repeated exposure to experimentally-induced insomnia symptoms. We postulate that there will be a progressive deterioration in the capability to inhibit pain (measured by the conditioned pain modulation test, resulting in **less habituation to pain** (as measured by pain intensity ratings to daily pain supra-threshold stimuli).

Aim 3 will investigate the **ability of the inflammatory and pain-inhibitory system to recover** from the effects of experimentally-induced insomnia symptoms. We postulate a progressive impairment of systems to return to baseline upon repeated exposure to insomnia symptoms.

B2. SIGNIFICANCE AND BACKGROUND FOR THE STUDY

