- (2) **Pain inhibition (Aim 2): Pain** is modulated and controlled by central, top-down pain-facilitatory and inhibitory circuits, which can dramatically increase or reduce (respectively) the intensity of a sensation³⁰. The capability to inhibit pain has been shown to contribute to the phenomenon of **pain habituation**. Specifically, painful stimuli administered on a daily basis result in substantially decreased pain ratings^{11;40} (habituation), and this effect has been linked to the activation of pain-inhibitory circuits⁶. The ability to habituate to daily aches and pains likely counteracts the process of sensitization and has been suggested to serve as a protective mechanism against the development of chronic pain^{32;36}. We postulate here that the failure to habituate to repeated (day-to-day) painful stimulation over the course of repeated exposure to a model of experimental insomnia is driven by a progressive deterioration in the capability to inhibit pain, which has previously been shown sensitive to short-term sleep disruption³⁷ as well as to insomnia disorder²¹.

[figure not shown]
Figure 1: Conceptual model of mechanistic pathways underlying the insomnia-pain relationship

In summary, we propose two processes by which repeated exposure to experimentally induced

insomnia promotes chronic pain vulnerability: (1) Increased sensitization of the nociceptive system via inflammatory dysregulation; (2) Decreased habituation to pain via failure of the pain-inhibitory system.

Do we recover from the effects of repeated exposure to experimental insomnia episodes (Aim

3)? Is a single night of good sleep in-between episodes of deficient sleep sufficient to reverse inflammatory and pain-inhibitory system changes? Or are more nights required? This is an important question designed to assess the elasticity or plasticity of systems in their attempt to return to normal functioning after exposure to sleep deficiency. **If these changes are more or less difficult to reverse by good sleep, this finding may urge to focus on the prevention of such changes, rather than treatment after change occurred.**

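### Aim 3 lists no contrast of day 17 with baseline or with the control stay, so its planned tests do not by themselves show whether recovery is complete

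*Combined protocol and SAP*

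**What the plan says.** Three places set out what Aim 3 is for:

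- B1 gives the hypothesis: "We postulate a progressive impairment of systems to return to baseline upon repeated exposure to insomnia symptoms".
- B2 puts the question behind it: "Is a single night of good sleep in-between episodes of deficient sleep sufficient to reverse inflammatory and pain-inhibitory system changes". It then asks whether more nights are needed.
- B3, Proposed Research Plan, says the protocol closes with four recovery nights "in order to statistically model time to obtain full recovery of the inflammatory and pain-inhibitory system".

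The analysis is in the Assessment of Aim 3 under Statistical Analysis. The mixed model is described as "utilizing four time points: baseline, and recovery at the end of 1st, 2nd, and 3rd insomnia episode", that is, days 3, 7, 11 and 15. The first set of contrasts reads: "To test this we will evaluate contrasts that compare IL-6 values at days 3 and 7, 7 and 11 and 11 and 15". Day 17 then enters once: "To test this we will evaluate the differences between other recovery days (average of days 7, 11, and 15) and day 17".

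On the model itself the plan says: "Data analysis for this aim is similar to data analysis described for Aim 1, but a different set of contrasts need to be defined". The Aim 1 text it refers to says: "Data will be used as it is or the difference between the two experimental conditions by episode will be used in the analysis". Neither section defines recovery or says how completeness of recovery will be judged.

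**The concern.** Whether one night is enough, and when recovery is full, are questions about how far a measure still lies from where it would have been without the insomnia nights. The natural references are day 3 and the same day of the control stay. Of the listed contrasts, only day 3 v day 7 uses baseline directly, and it covers only the first episode. The day 17 contrast uses earlier recovery days as its reference, and those may themselves be unrecovered.

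The control stay matters here. The B3 text on Visits 3 and 4 reports that inflammatory markers fell during control sleep in the research unit in earlier studies, and gives such unit effects as the reason for having a control condition. A within-stay comparison on raw values could therefore look like recovery when part of the fall is drift.

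At stake is the answer to the B2 question. B2 says that finding the changes hard to reverse may argue for a focus on prevention.

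**Working it through.** **Days.** Night 3 is baseline. Three four-night episodes fill nights 4–7, 8–11 and 12–15, so the single recovery nights are 7, 11 and 15. Four closing recovery nights within 18 nights are 15–18, and the third is 17. Days 3, 7, 11, 15 and 17 are all intensive recording days in both stays.

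**What the contrasts identify.** Let r7, r11, r15 and r17 be the change from day 3 on each day. The listed contrasts are:

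- C1 = r7
- C2 = r11 − r7
- C3 = r15 − r11
- C4 = (r7 + r11 + r15)/3 − r17

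| True state | C1 | C2 | C3 | C4 |
|---|---|---|---|---|
| Full recovery by day 7, maintained | 0 | 0 | 0 | 0 |
| Constant residual r through day 17 | r | 0 | 0 | 0 |
| Residual r at 7, 11, 15; half left at 17 | r | 0 | 0 | r/2 |
| Residual r at 7, 11, 15; none left at 17 | r | 0 | 0 | r |

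Only C1 separates the first two rows. A positive C4 occurs in both of the last two, so its significance does not distinguish partial from full return.

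The missing quantities can be recovered by combination: r15 = C1 + C2 + C3, and r17 = C1 + (2/3)C2 + (1/3)C3 − C4. The plan states neither, and the second needs day 17 in the same model.

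**Raw values or condition differences.** If the control stay drifts by δ between day 3 and day d, the raw insomnia-stay change equals the true residual plus δ. With δ negative, as the protocol reports for inflammatory markers, a raw change of zero is compatible with a true residual of −δ.

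**Illustration of what a null result would mean.** Inputs are the Table 1 means and SDs, N=26 and α=0.05. Assumptions: the test is two-sided, the SDs are those of paired differences, and they also apply to the residual. Power comes from the noncentral t distribution with 25 df and noncentrality d√26, where d = mean/SD. The plan's own figure, above 0.80 in every row, reproduces. The last two columns repeat the calculation at d/2.

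| Table 1 row | d | Power, full effect | Power, half effect | Half effect missed |
|---|---|---|---|---|
| Plasma IL-6, 1.95±1.59 | 1.226 | >99.9% | 85% | 15% |
| IL-6 positive monocytes, 38±66 | 0.576 | 80.6% | 29% | 71% |
| CPM, 47±54 | 0.870 | 98.9% | 57% | 43% |
| CPT habituation, −15±25 | 0.600 | 83.7% | 31% | 69% |
| CPT after recovery, −24±28 | 0.857 | 98.7% | 56% | 44% |

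The 95% CI half-width is 2.06 × SD/√26:

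- Plasma IL-6: 0.64 pg/mL
- Monocytes: 26.7 points
- CPM: 21.8 points

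With an observed residual of exactly zero, the interval would still admit residuals of 0.64/1.95 = 33%, 26.7/38 = 70% and 21.8/47 = 46% of the response.

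**The case against.** The planned tests suit the stated hypothesis. Aim 3 postulates impaired return to baseline, which is a difference hypothesis, and adjacent recovery-day contrasts address progression across episodes. That stands, and the listed contrasts should stay.

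A reader might infer that the trial will declare recovery whenever a contrast is not significant. The documents do not say so. The gap is that they give no other basis for a statement about completeness.

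A reader might also infer that control data play no part in Aim 3. That goes too far. Aim 3 borrows the Aim 1 framework, which focuses on comparing the two conditions and allows their difference to be analysed. If differences are used, day 3 v day 7 is already a baseline-adjusted comparison with control. But the text leaves the choice open, and even on differences the listed day 17 contrast still refers only to earlier recovery days.

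Aim 1 also mentions piecewise regression with a knot for the prolonged recovery at the end. It is optional and carries no recovery criterion.

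The miss rates are open to challenge. Half-sized residuals appear nowhere in the documents, and the SDs come from other sleep-loss protocols. A paired t-test stands in for a mixed model. Plasma IL-6 is reasonably sensitive. The one recovery-specific row in Table 1 shows a residual larger than the corresponding response (24 v 15 sec), which N=26 would detect with 98.7% power. So the figures show only how a null result could mislead; they do not forecast that it will. That same row is a comparison with control after recovery sleep, for which Aim 3 lists no counterpart.

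**Conclusion.** The point holds as a gap in specification. The documents ask whether recovery is sufficient and when it is full. The listed contrasts compare only day 7 directly with baseline, and none compares day 17 with day 3 or with the control stay. This follows from the contrasts themselves and needs no power assumption.

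The size of the risk if a null result were read as recovery depends on the outcome. For the primary or related measures in Table 1, a half-sized residual is missed from 15% (plasma IL-6) through 43% (CPM) to 71% (IL-6 positive monocytes) of the time, under the assumptions given with the table.

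A stronger reading would be that Aim 3 must be recast as an equivalence test with a fixed margin. The documents do not support that: they state a hypothesis of incomplete recovery and supply no margin. An estimate with its interval is enough to answer the question they ask.

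**What to change.** In the Assessment of Aim 3, add the insomnia-minus-control difference in change from day 3 at days 7, 11, 15 and 17, each with a 95% CI. Take these from the same mixed model, with day 17 added to the four time points now named. State that any conclusion about completeness of recovery, after one night or three, rests on that estimate and interval and not on a non-significant contrast. Keep the listed contrasts for progression and for one night against three. A recovery margin is optional and is for the sponsor to choose and justify.

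The cost is a few lines of analysis text and a few extra contrasts, with no new measurements. The drawback is that some intervals, notably for IL-6 positive monocytes and CPM, are likely to be too wide to settle whether recovery is complete, and the report would have to say so.
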